## 1. **INTRODUCTION**

This document describes the statistical methods and data presentations to be used in the summary and analysis of data from Protocol ATI-450-HS-201. Background information is provided for the overall study design and objectives. The reader is referred to the study protocol and case report forms (eCRFs) for details of study conduct and data collection.

The scope of this document excludes the analysis of biomarker data and exploratory endpoints.

### 1.1. **STUDY OVERVIEW**

This is a Phase 2a, randomized, double-blind, placebo-controlled study to investigate the efficacy, safety, tolerability, pharmacokinetics (PK), and pharmacodynamics (PD) of ATI-450 50 mg twice daily (BID) versus placebo in patients with moderate to severe HS.

The study will consist of an up to 28-day Screening Period, a 12-week treatment period, and a 30-day follow-up period. The total duration of the study for patients remaining until their final follow-up assessment will be up to 21 weeks. Patients will attend clinic visits on Days 1, 8, 15, 29, 43, 57, and 85 for safety, efficacy, PK, and PD assessments of the 12-week treatment period. A safety follow-up visit will be conducted 30 days after the last dose of study treatment for patients who completed the treatment period, as well as those who discontinue early.

Approximately 20 study centers in the United States are expected to participate in this study. Patients confirmed eligible at Baseline will be randomized in a 1:1 ratio to receive either ATI-450 tablets (50 mg BID) or matching placebo tablets BID. It is planned to randomize approximately 90 patients to obtain 45 patients per arm.

Study drug will be administered orally BID for 12 weeks. On clinic visit days, the morning dose of study treatment will be administered in the clinic.

The total duration of the study for patients remaining until their final follow-up assessment will be up to 21 weeks.

## 1.2. SCHEDULE OF ASSESSMENTS

Study Period 	Screening Period	Treatment Period							Follow-up Period
		Visit 1	Baseline Visit 2	Visit 3	Visit 4	Visit 5	Visit 6	Visit 7	
Visit Number (Visit Name)	Visit 1	Day 1 j	Day 8 j	Day 15	Day 29	Day 43	Day 57	Day 85 (Week 12/ET)	30 Days After Last Dose
Visit Window	NA	NA	± 1 Day						+ 7 Days
Assessmenti									
Informed Consent	X								
Eligibility Review	X	X							
Randomization		X							
Demographics	X								
Medical History; HS and Other Current Medical Conditions	X								
Lesion Count including AN and draining fistula (tunnels) count	X	X	X	X	X	X	X	X	X
NRS30 - Patient's Global Assessment Skin Pain (PGA-SP)		X	X	X	X	X	X	X	
DLQI Scale		X			X		X	X	
Hurley Stage Assessment	X	X	X	X	X	X	X	X	X
HS-PGA Scale	X	X	X	X	X	X	X	X	X
12-lead ECG a	X	X	X	X	X	X	X	X	
Vital Signs b	X	X	X	X	X	X	X	X	X
Body Weight, BMI (derived)	X								X

Study Period 	Screening Period	Treatment Period							Follow-up Period	
		Visit 1	Baseline Visit 2	Visit 3	Visit 4	Visit 5	Visit 6	Visit 7	Visit 8	
Visit Number (Visit Name)	Visit 1	Day 1 j	Day 8 j	Day 15	Day 29	Day 43	Day 57	Day 85 (Week 12/ET)	30 Days After Last Dose	
Visit Window	NA	NA	± 1 Day							+ 7 Days
Assessment										
Full Physical Exam Including Height	X									
Targeted Physical Exam		X	X	X	X	X	X	X	X	
Lesion Photography (optional)		X			X			X		
Laboratory Assessments: Hematology, Coagulation, Chemistry, Lipids, Urinalysis	X	X	X	X	X	X	X	X	X	
hsCRP	X	X	X	X	X	X	X	X	X	
HIV and Hepatitis B & C Screen	X									
SARS-CoV-2 Testing	X	X								
QuantiFERON Gold Test for TB	X									
Serum Pregnancy Test (WOCBP Only)	X									
Urine Pregnancy Test (WOCBP Only)		X	X	X	X	X	X	X	X	
Blood Sampling for PK		X c	X c	X c	X d	X d	X d	X c		
Dispense Study Drug		X	X	X	X	X	X			
Administration of Morning Dose of Study Drug in Clinic		X	X	X	X	X	X	X g		

Study Period g	Screening Period	Treatment Period							Follow-up Period
		Visit 1	Baseline Visit 2	Visit 3	Visit 4	Visit 5	Visit 6	Visit 7	
Visit Number (Visit Name)	Visit 1	Day 1 j	Day 8 j	Day 15	Day 29	Day 43	Day 57	Day 85 (Week 12/ET)	Visit 9 (EoS) 30 Days After Last Dose
Visit Day (Visit Week)	Day -28 to Day -1	Day 1 j	Day 8 j	Day 15	Day 29	Day 43	Day 57	Day 85 (Week 12/ET)	30 Days After Last Dose
Visit Window	NA	NA	± 1 Day						
Assessment									
Study Treatment Accountability			X	X	X	X	X	X	
Adverse Events h	X	X	X	X	X	X	X	X	X
Prior and Concomitant Medications	X	X	X	X	X	X	X	X	X

AE=adverse event; AN=abscess and inflammatory nodule count; BMI=body mass index; DLQI=Dermatology Life Quality Index; ECG=electrocardiogram;

ET=early termination; HIV=human immunodeficiency virus; HS=hidradenitis suppurativa; hsCRP=high sensitivity C-reactive protein;

HS-PGA=Physician Global Assessment Scale; mRNA=messenger RNA; NRS30= 30% reduction in Numerical Rating Scale for Patient's Global Assessment of Skin Pain (PGA-SP); PD=pharmacodynamic; PK=pharmacokinetic; SARS-CoV-2=severe acute respiratory syndrome coronavirus 2; TB=tuberculosis; WOCBP=women of childbearing potential.

- a. Triplicate 12-lead ECGs will be performed at least 30 seconds apart, in a supine position, after resting for at least 10 minutes (without external stimulation, e.g., talking, TV, noise) and submitted for central reading. Screening ECGs will be collected prior vital signs and blood samples. On Day 1 and 8, ECGs will be taken pre-dose and 2 hours post dose. Patients not fasting on Day 1 and 8 will have an additional 4 hr post dose ECG. On Days 15, 29, 43, 57, and 85, ECGs will be performed as the last assessment in the clinic (as close to Cmax). See Protocol Section 8.2.3 for additional details on collection parameters.
- b. Vital signs are to be taken before blood collection for laboratory tests. See Protocol Section 8.2.2 for additional details on collection parameters.
- c. PK blood sampling times on Days 1, 8, and 85 will occur pre dose and 2 hours after the morning dose. Patients not fasting on Days 1 and 8 will have an additional PK sample collected at 4 hours post dose. If the patient objects to both blood draws at the 2hr and 4hr timepoint, the 4hr PK sample is more important to collect. Patients must remain in the clinic until 30 minutes after the morning post dose PK blood sampling is completed. See Section 8.5 for additional details on collection parameters.
- d. PK blood sampling will occur prior to the morning dose on Days 15, 29, 43, and 57. See Protocol Section 8.5 for additional details on collection parameters.

[REDACTED]

[REDACTED]

[REDACTED]

[REDACTED]

g. The last dose of study treatment will be administered in the clinic on Day 85. The second dose of study treatment is not to be administered on Day 85.

- h. Serious AE reporting will start at the time of consent. Any AE that occurs between the time of consent and prior to dosing on Day 1 will be recorded as medical history. Treatment-emergent AEs will be collected following the first dose of study treatment on Day 1 through the Follow-up Visit (30 days after the last administration of study treatment) (Protocol Section 5.5).
- i. Unscheduled visits are allowed, as deemed necessary by the Investigator, if assessments need to be repeated (eg, lab draws), safety follow-up needs to be conducted, or additional dispensing activities need to occur.
- j. Patient should be fasted for visits on Days 1 and 8, defined as 8 hours since last food. A snack is permitted 2 hours after the morning dose.

## 2. **OBJECTIVES**

### **Primary Objective:**

The primary objective of this study is to assess the efficacy of ATI-450 in patients with moderate to severe HS

### **Secondary Objective:**

The secondary objectives are as follows:

- To assess the efficacy and safety of ATI-450 in patients with moderate to severe HS
- To assess the PK of ATI-450 in patients with moderate to severe HS

**Exploratory Objectives:** To assess the PD of ATI-450 in patients with moderate to severe HS

## 3. **GENERAL STATISTICAL CONSIDERATIONS**

### **3.1. SAMPLE SIZE AND POWER**

Approximately 90 patients will be randomized (approximately 45 per treatment group) to provide 90.3% power to demonstrate the superiority of ATI-450 to placebo in the reduction in inflammatory nodules and abscesses at Week 12. This power computation assumes that the reduction in the placebo arm will be on average 2.5 nodules/abscesses and the ATI-450 reduction will be on average 4.75 nodules/abscesses. A standard deviation of 3.6 was assumed for the number of nodules/abscesses. These sample size assumptions were based on the values observed in the adalimumab PIONEER I and PIONEER II Phase 3 trials (Frew et al, 2020, see Protocol Section 10.0).

### **3.2. RANDOMIZATION AND MASKING**

Patients will be randomized to study treatment in a 1:1 ratio to ATI-450 50 mg BID or placebo. All patients will be centrally assigned to randomized study treatment using an Interactive Voice/Web Response System (IxRS). Before the study is initiated, access instructions and directions for the IxRS will be provided to each study center.

This is a double-blind study with limited access to the randomization code. The ATI-450 and placebo tablets will be identical in physical appearance. The treatment each patient will receive will not be disclosed to the Investigator, study center staff, patient, or Sponsor. The treatment codes will be available to a limited number of third-party vendor personnel (IxRS administrative personnel, Clinical Supplies Management personnel, and unblinded Biostatistician) and Data Safety Monitoring Board (DSMB) members, as necessary, for them to support their functions on the study.

The IxRS will be programmed with blind-breaking instructions. In case of an emergency, the

---

Investigator has the sole responsibility for determining if unblinding of a patient's treatment assignment is warranted. Patient safety must always be the first consideration in making such a determination. If the Investigator decides that unblinding is warranted, the Investigator should make every effort to contact the study Medical Monitor prior to unblinding a patient's treatment assignment unless this could delay emergency treatment of the patient. If a patient's treatment assignment is unblinded, the study Medical Monitor must be notified within 24 hours after breaking the blind. The date and reason that the blind was broken must be recorded in the source documentation and eCRF, as applicable.

### **3.3. HANDLING OF DATA**

#### **3.3.1. Strata and Covariates**

There are no planned adjustments for strata.

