#### **3.3.2. Examination of Subject Subsets**

The following subject subsets are of interest.

- Baseline Hurley stage (mild, moderate, severe),
- Sex, and
- Baseline BMI category (underweight/normal [ $<25 \text{ kg/m}^2$ ], overweight [ $25 \text{ to } <30 \text{ kg/m}^2$ ], and obese [ $\geq 30 \text{ kg/m}^2$ ]).

The categorization of patients into a baseline Hurley stage will be based on the worst stage from the locations evaluated at the baseline assessment.

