## **5. STATISTICAL METHODS**

Descriptive statistical methods will be used to summarize the data from this study, with hypothesis testing performed for the primary and secondary efficacy endpoints. Unless stated otherwise, the term “descriptive statistics” refers to number of patients, mean, median, standard deviation, minimum, and maximum for continuous data, and frequencies and percentages for categorical data. For categorical variables, the denominator of percentages will be the number of patients with a

---

non-missing value at the visit and/or the scheduled time point. If a different denominator is used, this will be identified in the summary table.

All data collected during the study will be included in data listings. Unless otherwise noted, the data will be sorted first by treatment group, subject number, and then by date within each subject number. Assessments indicated as 'Not Done' will not be included in the listings.

The term 'treatment group' refers to all patients on the same dosing regimen. There will be two treatment groups in this study: Placebo BID and ATI-450 50mg BID.

All statistical testing will be one-sided and will be performed using a significance (alpha) level of 0.05 unless otherwise stated. P-values will be presented to three decimal places. For the efficacy endpoints, the ATI-450 treatment group will be tested versus Placebo via statistical inference.

The statistical analyses will be conducted with the SAS® software package version 9.4 or higher. All analyses will be subject to formal verification procedures. Specifically, results will be independently verified by a second programmer or statistician prior to issuance of the draft statistical report. All documents will be reviewed by the lead statistician to ensure accuracy and consistency.

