#### **5.4.2. Primary Efficacy Analysis**

Descriptive statistics for the count and change from baseline in the inflammatory abscesses and nodules will be presented for each scheduled analysis visit. This primary analysis will utilize the count with imputation for LOCF and will be based on the FAS population. Change from baseline in count of inflammatory abscesses and nodules up to Week 12 will be analyzed using a MMRM model. The model will include fixed effect terms for treatment, study visit, treatment by visit interaction and baseline count of inflammatory abscesses and nodules. Patient identifier will be included in the model in a manner that allows observations within a given patient over time to be treated as repeated measures. Within-subject variability will be modeled using a compound symmetry covariance structure. The LS Mean change from baseline in the count at each visit, estimated from the MMRM model, with the estimated standard error and 90% CI, will be presented in tabular and graphic format. The difference in the adjusted means between treatment groups and the associated 90% CI of the difference will be provided.

The model results from Week 12 are the primary efficacy analysis.

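### Neither the primary model nor the HiSCR50 model adjusts for worst baseline Hurley stage, already derived for each patient; adding it would give a small gain in precision and robustness.

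*SAP*

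**What the plan says.** **Allocation.** Protocol 6.3 and SAP 3.2 describe central 1:1 assignment through the IxRS and name no stratification factor. On the analysis side, SAP 3.3.1 states: "There are no planned adjustments for strata".

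**Primary model.** SAP 5.4.2: "The model will include fixed effect terms for treatment, study visit, treatment by visit interaction and baseline count of inflammatory abscesses and nodules". SAP 5.4.1.6 lists the same terms. For HiSCR50, SAP 5.4.5 specifies a Firth model with treatment and the baseline AN count.

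**Hurley stage.** It is assessed at Screening and Baseline (Protocol Table 1; SAP 1.2). SAP 3.3.2 makes it the first subset of interest and reduces it to one value per patient: "The categorization of patients into a baseline Hurley stage will be based on the worst stage from the locations evaluated". That baseline value then has two uses: a tabulation by arm (SAP 5.1), and a repeat of the primary MMRM within each stage where numbers allow (SAP 5.4.3; Tables 14.2.1.6.1 to 14.2.1.6.3).

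**The concern.** Hurley stage and the AN count measure different things. Protocol 8.1.5 grades tracts, scarring and extent of involvement. The AN count covers abscesses and inflammatory nodules only. Eligibility requires at least 5 such lesions and allows up to 20 draining fistulas, and the SAP plans tables for all three stages. Patients with the same baseline count may therefore differ a good deal in structural disease. For HiSCR50 the link is closer still, because response also requires no increase in draining fistulas.

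With about 45 patients per arm, the arms can differ by chance in Stage III share. If stage predicts the Week 12 change beyond what the baseline count explains, that part of an imbalance remains in the estimate for that trial. The within-stage models give up to three small-sample estimates rather than one adjusted difference. If the baseline table shows a marked imbalance, the SAP has no prespecified answer, and any adjustment made then would be post hoc.

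**Working it through.** **Inputs from the documents**
- Sample size: "Approximately 90 patients will be randomized (approximately 45 per treatment group" (SAP 3.1), so n = 45 per arm.
- Means: "the reduction in the placebo arm will be on average 2.5 nodules/abscesses" and "the ATI-450 reduction will be on average 4.75 nodules/abscesses" (SAP 3.1), so the difference is 4.75 − 2.5 = 2.25.
- SD: 3.6 (SAP 3.1).
- Test: one-sided, alpha 0.05 (SAP 5).

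**Inputs assumed, because the documents give none**
- Stage III share p: 30% to 50%.
- Residual effect g (fewer lesions improved in Stage III at the same baseline count): 1 to 2, with 3 as an outer case.
- Share of residual variance explained by Hurley stage, R²: 2% to 10%.
- The SD of 3.6 is treated as the residual SD of the change after baseline AN count. The SAP describes it only as the SD of the number of lesions.

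**Step 1: the plan's own figure.** SE = 3.6 × √(2/45) = 0.759. Noncentrality = 2.25 / 0.759 = 2.96. Noncentral t with 88 df, one-sided 0.05, gives 90.27%, which matches the stated 90.3%.

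**Step 2: precision gain.** Residual SD becomes 3.6 × √(1 − R²). The power column charges 2 df, slightly conservative for a two-level term.

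| R² | SE | Fall in SE, 1 − √(1 − R²) | Power |
|---|---|---|---|
| 0 | 0.759 | – | 90.3% |
| 2% | 0.751 | 1.0% | 90.8% |
| 5% | 0.740 | 2.5% | 91.5% |
| 10% | 0.720 | 5.1% | 92.7% |

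**Step 3: size of a chance imbalance.** SD of the between-arm difference in Stage III share = √(2p(1 − p)/45).
- p = 0.3: √(0.42/45) = 9.7 points; chance of at least 20 points in either direction, 3.8%.
- p = 0.4: √(0.48/45) = 10.3 points; 5.3%.
- p = 0.5: √(0.50/45) = 10.5 points; 5.8%.

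**Step 4: effect on the estimate.** Shift = imbalance × g. At 20 points:
- g = 1: 0.20 × 1 = 0.2 lesions, which is 9% of 2.25 and 0.26 SE.
- g = 2: 0.20 × 2 = 0.4 lesions, which is 18% of 2.25 and 0.53 SE.

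The two scales agree. At p = 0.4, g = 1 implies R² = 1 × 0.24 / 12.96 = 1.9%, and g = 2 implies 4 × 0.24 / 12.96 = 7.4%.

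**Step 5: validity.** A single-visit ANCOVA was simulated with 45 per arm, 40% Stage III and a correlation of 0.4 between latent severity and baseline AN. There were 20,000 runs under the null and 10,000 under the alternative.

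| g | Type I error without / with Hurley term | Power without / with |
|---|---|---|
| 1 | 5.0% / 5.0% | 90.2% / 90.4% |
| 2 | 5.0% / 5.0% | 90.0% / 91.5% |
| 3 | 4.9% / 4.9% | 90.1% / 93.8% |

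Under the null, the mean estimate is within 0.01 of zero in every case. In the roughly 8% of null runs with at least 15 points more Stage III on ATI-450, the unadjusted estimate shifts by 0.17, 0.35 and 0.53 lesions for g = 1, 2 and 3. With the Hurley term the shift is within 0.02 of zero.

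These are single-visit calculations. They do not reproduce the repeated-measures model with LOCF, and no corresponding figure was computed for HiSCR50.

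**The case against.** The strongest reply is that the planned model already adjusts for the baseline of the endpoint, itself a severity measure, and that this is a legitimate primary model for a 90-patient Phase 2a trial. Nothing in the documents says that Hurley stage predicts change in AN count once the baseline count is known, and sex and BMI are listed beside it as subsets of equal standing. The gain is 0.5 to 2.4 points of power on a plan already at 90.3%. The 4% to 6% chance of a 20-point imbalance counts both directions, so only about half of those trials would favour ATI-450. All of this stands. It fixes the point as minor, but does not remove it: a single Hurley-adjusted difference is still missing, and the variable is already derived.

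Four stronger readings are tempting, and the documents do not support them.
- *That allocation is simple randomisation.* Neither document says so. Blocking is neither stated nor excluded, and SAP 3.3.1 speaks of analysis, not of how the IxRS allocates.
- *That the plan ignores Hurley stage.* It tabulates stage by arm and fits the primary model within each stage.
- *That chance imbalance biases the result or inflates type I error.* Step 5 shows neither, because the standard error already covers chance imbalance.
- *That the cited source of the sample-size assumptions shows Hurley stage to be prognostic.* Its title in the reference list mentions associated covariates, but names none and says that they depend on the outcome measure.

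**Conclusion.** The point holds as a minor one about precision and robustness. Both models adjust for the baseline AN count alone, and no overall treatment difference adjusted for worst baseline Hurley stage is planned. The planned analysis remains valid without it.

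The likely benefit runs from negligible to modest: a 1% to 5% smaller standard error, and protection against a shift of 0.2 to 0.4 lesions in the few trials with a marked imbalance. Those sizes rest wholly on the assumed Stage III share and on the assumed prognostic strength beyond baseline count. If that strength is near zero, so is the benefit.

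**What to change.** Before unblinding, add worst baseline Hurley stage (I/II versus III) as a prespecified fixed effect to the primary MMRM in SAP 5.4.1.6 and 5.4.2 and to the HiSCR50 Firth model in SAP 5.4.5. Keep the AN-only model as a sensitivity analysis. Amend SAP 3.3.1 to match, and state there whether the IxRS stratifies. Leave randomisation unchanged.

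The cost is one model term and 1 degree of freedom, using a variable that the SAP already derives. The downside is little or no gain if Hurley stage adds nothing beyond the baseline count.

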#### **3.3.2. Examination of Subject Subsets**

The following subject subsets are of interest.

- Baseline Hurley stage (mild, moderate, severe),
- Sex, and
- Baseline BMI category (underweight/normal [ $<25 \text{ kg/m}^2$ ], overweight [ $25 \text{ to } <30 \text{ kg/m}^2$ ], and obese [ $\geq 30 \text{ kg/m}^2$ ]).

The categorization of patients into a baseline Hurley stage will be based on the worst stage from the locations evaluated at the baseline assessment.

#### **3.3.3. Multiple Testing and Comparisons**

There are no planned adjustments for multiple comparisons.

#### **3.3.4. Missing Data and Outliers**

Analysis visit windows will be applied as indicated in [Section 3.3.7](#). If an efficacy assessment is not available in an analysis visit window, then last observation carried forward (LOCF) will be applied to obtain a value for that analysis visit window for analyses conducted on the full analysis set population. For categorical efficacy endpoints, an additional sensitivity analysis will be conducted using non-responder imputation for cases where an efficacy assessment is not available in an analysis visit window. Missing data will not be imputed for safety summaries or efficacy summaries on the per protocol population.

There are multiple reasons that an assessment may not be available within an analysis visit windows:

- Clinic visits out of window or missed visits

- Data excluded from use in analysis due to confounding intercurrent event (see [Section 5.4.1.5](#))

For the latter reason, any assessments that occur after a confounding intercurrent event will be considered missing for purpose of analyses.

For analysis visit windows without an assessment, regardless of the reason, the last non-missing value prior to the start of the analysis visit window will replace the missing values. The baseline assessment can be carried forward.

If an AE has missing relationship to the study drug or severity, then that AE will be considered as ‘related’ to the study drug and the severity will be considered as ‘Severe’ in the table summaries, but the AE will be displayed as having a missing relationship or severity in the listings

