For this score, patients are defined as achievers or non-achievers. Patient achievers at any scheduled timepoint will have a HiSCR defined as at least a 50% reduction in abscess and inflammatory nodule count (AN count) and no increase in abscesses and no increase in draining fistulas relative to Baseline at that timepoint.

A patient is considered to be a HiSCR achiever only if all 3 criteria above are fulfilled ([Kimball et al, 2016b](#)).

The time required for Investigators to complete the HiSCR ranges from 1 to 2 minutes for patients with minimal disease, ie, 5 HS lesions in 2 anatomic locations, up to approximately 30 minutes for patients with multiple lesions in all 12 anatomic locations.

8.1.1.3 *International Hidradenitis Suppurativa Severity Score System*

The International Hidradenitis Suppurativa Severity (IHS-4) is a validated tool used to assess HS severity. The IHS-4 is calculated based on the clinical signs of HS: inflammatory nodules, abscesses and draining tunnels (fistulas and sinuses). The terms sinus tract and tunnel should be considered as synonyms of fistula ([Daxhelet 2020](#)).

The IHS-4 score (points) = (number of nodules multiplied by 1) + (number of abscesses multiplied by 2) + [number of draining tunnels (fistulas/sinuses) multiplied by 4].

A score of 3 or less signifies mild HS, a score of 4-10 signifies moderate HS and a score of 11 or higher signifies severe HS ([Zouboulis et al, 2017](#)).

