9.4.4 Missing Data

Missing data will not be imputed for the safety summaries, or the efficacy summaries conducted on the PP population. All efficacy analyses conducted on the FAS population will use a LOCF analysis. Additionally, a sensitivity analysis will be conducted for categorical endpoints conducted on the FAS using the non-responder imputation method. Further details regarding the imputation of data that are missing or following intercurrent events will be provided in the SAP.

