##### **5.4.1.5. Intercurrent Event Strategy**

Prior to week 12 lesion counts, the following are confounding intercurrent events that are likely to occur in some patients during conduct of the trial: 1) discontinuation of study treatment for any reason, 2) the administration of protocol prohibited medications listed in Appendix 5 of the

---

Protocol that could impact efficacy for any reason, and 3) surgical intervention. Determination of prohibited medications that could impact efficacy will be conducted in a blinded manner prior to database lock. Assessments that occur after a confounding event will be excluded from the analysis and imputed using the last observed assessment prior to the intercurrent event. The date/time of the confounding event and the start date/time of imputation will be determined based upon the last dose of study medication, the start date of any relevant prohibited medications, and the start date of any surgical procedures.

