##### Logistic Analyses

For each treatment group, the observed achiever/responder rate for HiSCR50, [REDACTED], NRS30 and [REDACTED] will be reported along with the 90% CI for the response rate using the normal approximation. The difference in observed response rates will also be presented.

---

The percentage of patients achieving HiSCR50, [REDACTED], NRS30, and [REDACTED] at Week 12 and each scheduled analysis visit will be assessed using a Firth's penalized likelihood logistic regression model with fixed effect for treatment and an applicable baseline as a covariate. For HiSCR50, [REDACTED], and [REDACTED], the baseline covariate will be the count of inflammatory abscesses and nodules. For NRS30, the covariate will be the baseline PGA-SP. The analysis on the FAS population will use LOCF for missing values. An additional sensitivity analysis will be conducted for all of these responder endpoints except [REDACTED] where missing will be imputed as non-response.

Inferential results will include model-based responder estimates and associated 90% CIs, differences in estimates and associated 90% CIs for the active group versus placebo, and p-values testing for significance in the difference.

All efficacy data will be presented in data listings.

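### The main HiSCR50 and NRS30 analyses carry a pre-event response past drug stop, confounding medication or surgery to Week 12; non-response is only the sensitivity analysis

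*SAP*

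**What the plan says.** Protocol 9.4.4 sets the general rule: "All efficacy analyses conducted on the FAS population will use a LOCF analysis". It adds non-responder imputation as a sensitivity analysis for categorical endpoints. SAP 3.3.4 follows the same order. For a visit without an assessment, its FAS rule reads: "then last observation carried forward (LOCF) will be applied to obtain a value for that analysis visit window for analyses conducted on the full analysis". It treats post-event data in the same way: "any assessments that occur after a confounding intercurrent event will be considered missing for purpose of analyses". The replacement is general: "regardless of the reason, the last non-missing value prior to the start of the analysis visit window will replace the missing values". Baseline may be carried forward too.

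SAP 5.4.1.5 names the events: stopping study treatment for any reason, prohibited medication that could affect efficacy (judged blind), and surgery. Later values are "imputed using the last observed assessment prior to the intercurrent event". That list sits under the primary estimand, but SAP 3.3.4 cross-refers to it for efficacy assessments in general, so it also governs the responder endpoints.

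For those endpoints SAP 5.4.5 (Logistic Analyses) says: "The analysis on the FAS population will use LOCF for missing values". On the alternative, SAP 3.3.4 says: "For categorical efficacy endpoints, an additional sensitivity analysis will be conducted using non-responder imputation for cases where an efficacy assessment is not available". SAP 5.4.5 repeats this but exempts a redacted item. SAP Section 9 lists non-response tables for HiSCR50 (14.2.2.2) and NRS30 (14.2.5.2). Tables 14.2.3 and 14.2.4, for HiSCR at redacted criteria, are listed with LOCF only.

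**The concern.** HiSCR is a status at a visit. Protocol 8.1.1.2 says: "Patient achievers at any scheduled timepoint will have a HiSCR defined as at least a 50% reduction in abscess and inflammatory nodule count", with no rise in abscesses or draining fistulas, all judged at that timepoint. Under the SAP, a Week 6 status can be reported as the Week 12 status of a patient who has since stopped drug or been treated with something else.

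SAP 5.4.1.2 places excluded medication, given as rescue or after stopping drug, outside the treatment condition of interest. For the primary estimand it also places treatment shorter than 12 weeks outside. No separate estimand is written for the responder endpoints, yet their main analysis can credit such patients with Week 12 success. Protocol 7.1 prefers that patients who stop drug keep attending visits, so an observed Week 12 non-response may exist and be overwritten by an earlier response.

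At stake is the Week 12 rate in each arm for the first-listed secondary endpoint and for NRS30, and possibly the difference between arms, which is tested one-sided at 0.05.

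**Working it through.** **The plan's own figure.** The only power stated is for the primary endpoint: 45 per arm, difference 4.75 - 2.5 = 2.25, SD 3.6, one-sided alpha 0.05. The standard error is 3.6 x sqrt(2/45) = 0.759, and 2.25/0.759 = 2.965. Normal power is Phi(2.965 - 1.645) = 90.65%. The t version with 88 df gives 90.27%, which matches the stated 90.3%. No response rate, event rate or power is given for HiSCR50 or NRS30.

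**How the rules score a patient at Week 12:**

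| Patient | Main (LOCF) | Planned sensitivity (non-response) | Proposed main |
|---|---|---|---|
| Achiever on Day 43, then stops drug; Day 85 counts no longer meet HiSCR50 | Achiever | Non-achiever | Non-achiever |
| Non-achiever on Day 43, then stops drug | Non-achiever | Non-achiever | Non-achiever |
| Event before any post-baseline visit (baseline carried) | Non-achiever | Non-achiever | Non-achiever |
| Achiever on Day 57, misses Day 85, no event | Achiever | Non-achiever | Achiever |

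Only the first row is at issue: patients who were achievers at the last pre-event visit.

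**Size.** For one arm, let d be the share with an event before the Week 12 count, q the share of those who were achievers at the last pre-event visit, and r the response rate in event-free patients. Ignore visits missed without an event.

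- LOCF rate = (1 - d) x r + d x q
- Rate with events as non-response = (1 - d) x r
- Excess in the arm = d x q
- Shift in the difference = (d x q on ATI-450) - (d x q on placebo)

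All values of d and q below are assumptions.

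| ATI-450 d x q | Placebo d x q | Shift in difference |
|---|---|---|
| 15% x 30% = 4.5 points | 15% x 30% = 4.5 points | 0 |
| 20% x 40% = 8.0 points | 10% x 25% = 2.5 points | +5.5 points |
| 30% x 50% = 15.0 points | 10% x 30% = 3.0 points | +12.0 points |
| 10% x 30% = 3.0 points | 30% x 30% = 9.0 points | -6.0 points |

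In the first row, 4.5 points is 0.045 x 45 = 2.0 patients per arm. Over d = 10% to 30% and q = 20% to 50%, the excess per arm runs from 2 points (0.9 of 45 patients) to 15 points (6.8 of 45).

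**Effect on the test.** This uses an exact calculation with 45 per arm and a pooled two-proportion z test, one-sided 0.05, in place of the planned Firth model. Assume equal response (25% to 35%) among event-free patients in both arms.

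- ATI-450 20% x 40% against placebo 10% x 25%: LOCF rejects in 7.5% to 9.8% of trials, non-response in 2.3% to 2.9%.
- ATI-450 25% x 40% against placebo 10% x 25%: LOCF 7.9% to 11.2%, non-response 1.5% to 2.0%.
- Events 10% on ATI-450 and 20% on placebo: non-response itself rejects in 9.3% to 10.3%.

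Neither rule holds 5% under this null when event rates differ. The non-response rule counts the event as part of the outcome, so a difference in events becomes a difference in response.

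**The case against.** The strongest reply is that the alternative result is already planned. Because post-event data are treated as missing, the non-response tables for HiSCR50 and NRS30 already score these patients as non-achievers. PP tables (14.2.2.3 and 14.2.5.3), limited to patients who stay on drug and have a Week 12 count, are listed as well. Protocol and SAP agree on the order, and these are supportive secondary endpoints in a Phase 2a trial without multiplicity control. All of this stands, and it limits the point to which analysis is called main.

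It can also be said that Protocol 8.1.1.2 is a scoring definition and not a missing-data rule, and that SAP 5.4.1.2 does not equate an event with non-response. That is fair: counting events as failures is a choice of estimand. The proposed rule also departs from observed status, since a patient who still meets HiSCR at Week 12 after stopping drug becomes a non-achiever.

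Three stronger readings are tempting but not supported:

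- **Treatment failures in general are counted as responders.** Only pre-event achievers are; a pre-event non-response or baseline value carries forward as non-response. Discontinuation counts for any reason, so it is not the same as failure.
- **LOCF inflates false positives in favour of ATI-450 by a known amount.** No input is in the documents, and the sign can reverse. Fixing the share of all randomised patients who are event-free responders as equal gives larger rejection rates, but that makes non-response correct by construction.
- **The LOCF-only Tables 14.2.3 and 14.2.4 are an oversight.** They may be the redacted exemption in SAP 5.4.5. What can be said is that SAP 3.3.4 states no exemption and SAP 5.4.5 does.

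**Conclusion.** The point holds as a matter of which analysis leads. As written, the main Week 12 HiSCR50 and NRS30 rates include patients whose response was last seen before they stopped drug, took confounding medication or had surgery. Each arm's rate exceeds its non-response counterpart by d x q: 4.5 points at an assumed 15% x 30%, and 2 to 15 points over the assumed ranges. The difference between arms is unchanged when d x q is equal, and moved by -6 to +12 points in the cases shown. It cannot be called biased towards ATI-450 in advance.

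The change is worth making because the headline rate would otherwise describe something other than Week 12 response on a 12-week regimen, and the correction is cheap. It does not reach the primary AN-count test or its power.

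**What to change.** In SAP 3.3.4 and 5.4.5, for HiSCR50 and NRS30:

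1. Make the main FAS rule non-achiever at every visit after a confounding intercurrent event.
2. Use LOCF only for a missed or out-of-window visit with no such event.
3. Keep the present all-LOCF analysis as the sensitivity analysis.
4. Align Protocol 9.4.4, or record the departure in SAP Section 6.

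For Tables 14.2.3 and 14.2.4, reconcile SAP 3.3.4 with the exemption in SAP 5.4.5, and add the non-response version unless the exemption is deliberate. Do not extend the rule to the lesion-worsening endpoint in Protocol 9.4.1 (at least a 25% rise in AN count). There, imputing non-response would record no worsening and so act in the wrong direction.

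The cost is SAP wording and one derivation flag, since event dates are already derived and non-response outputs are already planned for both endpoints. Reported rates will be somewhat lower, and a patient observed to respond after stopping drug will count as a non-achiever. The retained LOCF analysis does not show that patient's observed status either, so the listings should.
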